#### **4.10 Study Discontinuation and Closure**

This study may be temporarily suspended or prematurely terminated if there is sufficient reasonable cause (as determined by the MCW study PI, DSMC, sponsor, and/or IRB). Written notification, documenting the reason for study suspension or termination, will be provided by the suspending or terminating party to study participants, investigator, funding agency, the Investigational New Drug (IND) sponsor and regulatory authorities. If the study is prematurely terminated or suspended, the MCW principal investigator (PI) will promptly inform the MCW Institutional Review Board (IRB), and the sponsor and will provide the reason(s) for the termination or suspension. Study participants will be contacted, as applicable, and be informed of changes.

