### 5.7 Dose Modifications

As indicated in the study calendar, a complete metabolic panel (including LFTs) will be performed mid-way during the course of ATB. Adverse events will be graded according to CTCAE v.5.

Adverse Event (CTCAE, v. 5)	Action
Non-hematological, grade 1 or 2	Continue ATB therapy at full dose prescribed. Apply maximum supportive care recommendations. If persistent duration of grade 2 adverse event is affecting quality of life, a one-time decrease of 25%.
Non-hematological, grade 3 or 4	
Apply maximum supportive care recommendations. Hold ATB therapy until recovery to grade <math>\leq 1</math> (up to 7 days).
 
If concomitant elevation of AST/ALT 3 times the upper limit of normal and bilirubin elevation 2 times the upper limit of normal (Hy's Law criteria) the patient must be removed from study treatment, ATB must be permanently discontinued.
 
If recurrence of adverse event after drug hold and/or interruptions is observed and maximum supportive care measures applied, a dose reduction by 25% is recommended. ATB should not be used at doses below 50%

Non-hematological, grade 3 or 4 and adverse events NOT resolved to grade $\leq 2$ within a maximum of 14 calendar days from last planned administration	Dose reductions by 25% (up to 2 reductions) will be considered after maximum supportive care recommendations are introduced.

Dose Level	Dose
-2	600 mg TID
-1	900 mg TID
0	1200 mg TID

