## 6.2 Collection and Reporting Requirements for Adverse Events and Serious Adverse Events

### 6.2.1 Collection of Adverse Events

All (or specify if only certain grade AE needed) adverse events (including SAEs) must be recorded in OnCore® and/or an adverse event log. All AEs required to be collected must be graded according to the CTCAE v5. When possible, signs and symptoms indicating a common underlying pathology should be noted as one comprehensive event. Investigator's or treating physician's assessment of AE attributions must also be documented.

AEs will be collected from the time the subject signs the consent form through 30 days post last dose of study drug(s). AEs will be tracked and followed until resolution, subject withdraws consent, or is lost to follow-up (including subjects who discontinue early). All adverse events collected per the protocol will be followed with appropriate medical management until they are resolved, if they are related to the study treatment, or until the investigator deems the event to be chronic.

Please see section 6.2.2 and table 4 to identify the adverse events that need to be reported.

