### 6.5 Safety Assessment

Dose-limiting toxicity (DLT) is defined as the occurrence of any grade  $\geq 3$  adverse event (AE) that is definitely or probably related to ATB and occurs during the study.

An early safety assessment will be performed after the first four patients complete protocol therapy and reported to the DSMC. In the event of 0-1 DLT events, the experimental therapy is considered safe and the study will proceed to the second cohort of four patients. In the event of  $\geq 2$  DLTs in the first four patients, the study chairs and DSMC will recommend proceeding with the second cohort at dose level -1 or dose level -2.

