### **8.2 Study Team**

The study team minimally consists of the principal investigator, the clinical research coordinator, regulatory specialist, and the study biostatistician. While subjects are on study, the principal investigator will meet regularly with the research coordinator and the study biostatistician to review study status. This review will include but not be limited to reportable SAEs and UPIRSOs and an update of the ongoing study summary that describes study progress in terms of the study schema. The appropriateness of further subject enrollment and the specific intervention for a next subject enrollment is addressed. All meetings including attendance are documented.

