## 8.5 DSMC

The Medical College of Wisconsin Cancer Center places the highest priority on ensuring the safety of patients participating in clinical trials. Every cancer interventional trial conducted at MCW includes a plan for safety and data monitoring.

More information can be found related to the MCWCC Data and Safety Monitoring Plan at the MCWCC website ([Data and Safety Monitoring Plan](#)).

This study will be reviewed by the Medical College of Wisconsin Cancer Center Data and Safety Monitoring Committee (MCWCC DSMC). A summary of the MCWCC DSMC activities are as follows:

- Review the clinical trial for data integrity and safety
- Review all DSM reports
- Submit a summary of any recommendations related to study conduct
- Terminate the study if deemed unsafe for patients

A copy of the MCWCC Data and Safety Monitoring Plan and membership roster will be maintained in the study research file and updated as membership changes. The committee will review reports from the study PI twice annually (or more frequently if needed) and provide recommendations on trial continuation, suspension, or termination as necessary.

Any available DSMC letters will be submitted to the IRB of record as required.

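### Section 6.5 tests its two-DLT threshold only after four patients complete therapy, so later first-cohort patients may still start at 1,200 mg TID after it is met

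*Combined protocol and SAP*

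**What the plan says.** Section 6.5 defines a DLT as a grade 3 or higher adverse event that is probably or definitely related to ATB. It gives one look: "An early safety assessment will be performed after the first four patients complete protocol therapy and reported to the DSMC". The two outcomes are:

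- Favourable: "In the event of 0-1 DLT events, the experimental therapy is considered safe", and the second cohort of four follows.
- Unfavourable, meaning two or more DLTs among those four: "the study chairs and DSMC will recommend proceeding with the second cohort at dose level -1 or dose level -2".

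Section 6.5 says nothing about first-cohort patients who have not yet started, and it sets no stagger between patients. Section 5.1 fixes the dose at 1,200 mg three times daily; Section 5.7 gives level -1 as 900 mg and level -2 as 600 mg TID.

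Other provisions bear on the same decision:

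- Section 8.2: the study team meets regularly, and "The appropriateness of further subject enrollment and the specific intervention for a next subject enrollment is addressed".
- Section 4.10: "This study may be temporarily suspended or prematurely terminated if there is sufficient reasonable cause", as judged by the investigator, DSMC, sponsor or IRB.
- Section 8.5: the DSMC reviews reports twice a year, or more often if needed, and can terminate the study.
- Table 4 (Section 6.2.2): unexpected related SAEs, related grade 4–5 SAEs and grade 4 AEs go to the DSMC within 5 calendar days. Unexpected non-serious grade 3 AEs get routine review.
- Section 5.7: ATB is held at grade 3–4 and stopped on Hy's Law criteria, and "a complete metabolic panel (including LFTs) will be performed mid-way during the course of ATB". These measures act on the patient who has the event.
- Section 4.6 mentions study stopping rules, but none is defined.

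**The concern.** A count of DLTs among four patients can only rise. Once two patients have had one, the condition for lowering the dose is satisfied whatever happens to the others. Section 6.5 nevertheless waits until all four have completed therapy and then acts only on the second cohort. One or two further patients may therefore start at the dose that has already met the protocol's own threshold.

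These patients are awaiting definitive cancer surgery and the sole objective is pharmacokinetic, so a full-dose start after that point needs a reason, and the plan gives none.

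The routes that could prevent it depend on judgement. Table 4 brings many serious or grade 4 events to the DSMC quickly, but it does not count DLTs or require a pause. A non-serious, unexpected grade 3 event can be a DLT and still reach the DSMC only at scheduled review.

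The unit is also unclear. Section 6.5 speaks of DLT events in one branch and of DLTs in the first four patients in the other. If events are counted, two in patient 1 would meet the threshold with three starts still to come.

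**Working it through.** **The plan's own figure.** Section 7.1 assumes an SD of 50% of the mean and six analyzable patients. The half-width is t(0.975, 5) × 0.5/√6 = 2.571 × 0.5/2.449 = 52.5% of the mean, as stated. The plan gives no operating characteristics for the DLT rule.

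**Inputs.** The threshold is two, among four patients (6.5). Accrual is eight patients in about one year (3.2, 3.3), or 52/8 = 6.5 weeks per patient on average. A course lasts 7–28 days (5.1), and AE collection runs to 30 days after the last dose (6.2.1). The DLT rate p is an assumption, taken as 5, 10, 20 and 30%, with independent patients and at most one DLT counted per patient.

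**Sequential patients (exact binomial).**

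- Met before patient 4 starts: P(≥2 of 3) = 3p²(1−p) + p³.
- Met before patient 3 starts: p².
- Expected avoidable starts: P(≥2 of 3) + p².
- Threshold met at all: P(≥2 of 4) = 1 − (1−p)⁴ − 4p(1−p)³.

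At p = 10%: 0.027 + 0.001 = 0.028 before patient 4; 0.010 before patient 3; 0.038 avoidable starts. P(≥2 of 4) = 1 − 0.6561 − 0.2916 = 0.0523, and 0.028/0.0523 = 54%.

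**Overlapping courses (simulation, at least 2 million trials per setting).** Gaps between starts are exponential with mean 6.5 weeks. Three timings were used: (a) course uniform on 1–4 weeks, DLT uniform within it; (b) the same course, DLT uniform over the course plus 30 days; (c) every course 28 days, DLT known only at its end. Simulation error is about 0.1 percentage point or less.

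| Assumed DLT rate | 5% | 10% | 20% | 30% |
|---|---|---|---|---|
| P(≥2 of 4) | 1.4% | 5.2% | 18.1% | 34.8% |
| Met before patient 4 starts: sequential | 0.7% | 2.8% | 10.4% | 21.6% |
| – overlap (a) | 0.6% | 2.5% | 9.2% | 19.3% |
| – overlap (b) | 0.5% | 2.0% | 7.4% | 15.6% |
| – overlap (c) | 0.5% | 1.8% | 7.0% | 14.7% |
| Avoidable full-dose starts: sequential | 0.010 | 0.038 | 0.144 | 0.306 |
| – overlap (c), the lowest | 0.006 | 0.024 | 0.09 | 0.20 |
| Share of trials with ≥2 of 4 that meet it before patient 4: sequential | 52% | 54% | 58% | 62% |
| – overlap (c), the lowest | 34% | 35% | 38% | 42% |

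The last two rows are conditional on at least two of the four patients having a DLT at any time, including after the fourth completes. With sequential patients and p of 1% or 2%, the threshold is met before patient 4 in 0.03% or 0.12% of trials.

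**PK precision at 1,200 mg** under 7.1's SD assumption, t(0.975, n−1) × 0.5/√n: n = 4, 3.182 × 0.25 = ±79.6%; n = 3, 4.303 × 0.5/1.732 = ±124%; n = 2, 12.706 × 0.5/1.414 = ±449%.

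**The case against.** The strongest reply is that the decision is already provided for. In a single-site study of eight patients, the team meets regularly, documents its meetings and must address the next patient's intervention. For most serious DLTs the DSMC hears within 5 calendar days and can terminate. Harm would require the investigator, the team, the DSMC and the IRB all to let pass two grade 3 or higher events attributed to ATB in two or three patients. This largely stands, and it limits the weight of the point. It does not remove it: none of these routes has a DLT count attached, and the fastest one does not cover unexpected non-serious grade 3 events.

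A second reply is that the event is improbable. Section 1.1 reports no toxicity in 300 participants at 4,800 mg/d for six months, a higher dose for much longer. It also calls the toxicity reporting in the earlier trials qualitative. Nothing in the documents supports a rate of 20–30%. At 5% and 10%, multiplying sequential avoidable starts by the rate gives at most 0.010 × 0.05 = 0.0005 and 0.038 × 0.10 = 0.0038 DLTs averted per trial, even if a lower dose removed all toxicity. That stands too.

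Two stronger readings are tempting. A reader might infer that the protocol obliges remaining first-cohort patients to start at full dose, or leaves them unprotected. The documents do not support this: Sections 4.10, 8.2 and 8.5 allow a pause or a changed intervention, and Section 5.7 protects each treated patient. A reader might also take the one-third to three-fifths share as the chance of trouble in this trial. It applies only to the uncommon trials in which at least two of the first four patients have a DLT.

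**Conclusion.** The gap is real but small, and worth closing because closing it is cheap. The only DLT-count rule is tested once and acts only on the second cohort, so it can be met while one or two more patients start at the dose that met it.

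In absolute terms this is unlikely: under 3% of trials if the DLT rate is 10% or lower, rising to 14.7–21.6% only at an assumed 30%. The conditional share shows how the rule performs when it is needed. Where at least two of the first four patients have a DLT, between about a third and three-fifths of trials would already have met the threshold before patient 4 starts. That share varies little with the DLT rate and more with how far courses overlap.

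The textual reading is secure. The probabilities rest on assumed DLT rates, independent patients, at most one counted DLT per patient and steady accrual over one year. They are illustrative, and they do not show that the trial is unsafe.

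**What to change.** Replace the single look in Section 6.5 with wording such as:

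> Patients with at least one DLT are counted as they occur among the first four patients who receive ATB. When a second such patient has a DLT, the DSMC is notified within 5 calendar days whatever the event's seriousness or expectedness, and no new patient starts ATB until the study chairs and DSMC have made an ad hoc recommendation. The recommended dose level (-1 or -2) applies to every patient not yet started, in either cohort. Otherwise the early assessment is made when those same four patients have completed or discontinued ATB.

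The amendment should disclose two changes of definition. The unit becomes patients with a DLT, not DLT events. The denominator becomes the first four treated, not the first four who complete; a patient taken off ATB for a DLT might otherwise fall outside it. The threshold of two and the dose levels stay as they are. Ad hoc review already fits Section 8.5, and patients already on ATB remain under Section 5.7.

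The cost is one paragraph, plus the following only if the rule fires early:

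- **A short accrual hold.** Any deadline for the recommendation is the sponsor's choice. Each week of hold delays on average 1/6.5 = 0.15 new patients. A patient already registered could be lost, because ATB should start within seven days of registration. The no-replacement rule in Section 4.6 covers only patients who received the intervention, so it does not bar replacing that patient.
- **Fewer full-dose profiles.** There would be two or three at 1,200 mg instead of four, with a 95% half-width of ±449% or ±124% against ±79.6%. Six profiles at 1,200 mg (±52.5%) are already out of reach under the current plan once the threshold is met, so that loss is not a cost of the change.

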**Table 4**

Attribution	SAE				AE		
	Grade 1, 2 & 3		Grade 4 and 5		Grade 3	Grade 4	
	Expected	Unexpected	Expected	Unexpected	Unexpected	Expected	Unexpected
Unrelated Unlikely	IRB  and DSMC  - Routine Review 	IRB  and DSMC  - Routine Review 	IRB  - Routine Review 	IRB  - Routine Review 	DSMC  - Routine Review 	DSMC  - Within 5 calendar days	DSMC  - Within 5 calendar days
Possible Probable Definite		IRB  and DSMC  - Within 5 calendar days	DSMC  - Within 5 calendar days	IRB  and DSMC  - Within 5 calendar days			

1. Guidance on adverse event reporting to the IRB is available online at MCW IRB Policies and Procedures.
2. For expedited DSMC reporting, study coordinator/research nurse must notify the DSMC via email including the subject ID, date of event, grade, relatedness, expectedness, and a short narrative. DSMC will review data entered into OnCore®.
3. For routine reporting, the events will be reported to IRB as part of the annual continuing progress report and the DSMC will review data entered into OnCore® at the time of scheduled monitoring.
4. Fatal or life-threatening SAEs meeting the criteria indicated in the above table will be reported to FDA no later than seven calendar days after study staff's initial awareness of the event. If the SAE is not fatal or life-threatening and meets the above criteria, the timeline for submitting an IND safety report to FDA is no later than 15 calendar days after study staff's initial awareness of the event. See section 6.2.3 for detailed reporting instructions.

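### The four-patient DLT rule in 6.5 has no explicit stop or enrolment hold, and at 2 or more DLTs it fixes the DSMC's advice in advance, which is inconsistent with 8.5

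*Combined protocol and SAP*

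**What the plan says.** Section 6.5 defines a DLT as any adverse event of grade 3 or higher that is definitely or probably related to ATB. Grade 5 is therefore included. There is one planned look, after the first four of the eight patients complete therapy, and it has two branches.

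- **0-1 DLT events:** "In the event of 0-1 DLT events, the experimental therapy is considered safe and the study will proceed to the second cohort".
- **2 or more DLTs:** "the study chairs and DSMC will recommend proceeding with the second cohort at dose level -1 or dose level -2". Section 5.7 gives these levels as 900 mg and 600 mg three times daily, against a starting dose of 1,200 mg.

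Section 8.5 describes the same committee's role in open terms. It is to "provide recommendations on trial continuation, suspension, or termination as necessary", and its listed activities include "Terminate the study if deemed unsafe for patients". Section 4.10 adds a general power: "This study may be temporarily suspended or prematurely terminated if there is sufficient reasonable cause", as judged by the PI, DSMC, sponsor or IRB.

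**The concern.** The four-patient look is the one planned point at which DLTs are added up across patients. A rule at that point should let the committee choose among stopping, pausing, lowering the dose and continuing. As written, 6.5 offers only continuing at full dose or continuing at a lower dose.

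Two consequences follow. First, at 2 or more DLTs the recommendation is settled before the committee sees the number, type or grade of events. A DSMC that wished to recommend termination after four affected patients would have to depart from 6.5 and rely on 8.5, and the protocol does not say which section governs. Second, the lower branch turns on the count alone. One death judged definitely or probably related to ATB is one DLT event, and the text then labels the therapy safe. The participants are awaiting definitive cancer surgery and the objective is pharmacokinetic, so there is little reason to commit to a second cohort in advance.

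**Working it through.** Section 6.5 states no DLT rate, error rate or power, so there is no figure of the plan's own to reproduce. The check is to list the outcomes, compare the sections, and gauge how often the upper branch would be reached.

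**1. Outcomes under 6.5.** Inputs: n = 4 at the look, with the two branches as written. The exact (Clopper-Pearson) 95% interval for the DLT rate uses a lower limit of Beta quantile(0.025; x, n-x+1) and an upper limit of Beta quantile(0.975; x+1, n-x). For 4/4 the lower limit is 0.025^(1/4) = 0.398.

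| Patients with a DLT (one event each) | Action in 6.5 | Exact 95% interval |
|---|---|---|
| 0 of 4 | safe; second cohort | not needed here |
| 1 of 4 | safe; second cohort | 0.6% to 80.6% |
| 2 of 4 | second cohort, level -1 or -2 | 6.8% to 93.2% |
| 3 of 4 | second cohort, level -1 or -2 | 19.4% to 99.4% |
| 4 of 4 | second cohort, level -1 or -2 | 39.8% to 100% |

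All five outcomes lead to a second cohort. Grade enters only through the threshold of 3, so a grade 5 event carries the same weight as a grade 3 event. The intervals are wide because four patients are few. They show that one count of 1 cannot establish safety, and that results as different as 2/4 and 4/4 receive the same instruction.

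**2. Other provisions that could supply the missing outcome.**

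- Section 5.7 acts on the individual. Under Hy's Law criteria "the patient must be removed from study treatment, ATB must be permanently discontinued", but this does not affect enrolment.
- Table 4 sets reporting duties. It sends related serious events of grade 4-5, and unexpected related serious events of grade 1-3, to the DSMC within 5 calendar days. Its notes and 6.2.3 require FDA reporting of related, unexpected, serious events, within 7 calendar days if fatal or life-threatening and otherwise within 15.
- Section 8.2 has the study team review enrolment as it goes: "The appropriateness of further subject enrollment and the specific intervention for a next subject enrollment is addressed".
- Sections 8.5 and 4.10 allow termination or suspension.

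None of these uses the DLT count. Outside 6.5, DLT appears only in the abbreviation list.

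**3. How often the upper branch is reached.** The documents give no DLT rate, so p is assumed. Counting patients, P(2 or more of 4) = 1 - (1-p)^4 - 4p(1-p)^3:

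- p = 10%: 1 - 0.6561 - 0.2916 = 0.0523
- p = 20%: 1 - 0.4096 - 0.4096 = 0.1808
- p = 30%: 1 - 0.2401 - 0.4116 = 0.3483

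Counting events requires a further assumption. With Poisson events and the same chance p of at least one event per patient, the total mean is m = -4 ln(1-p), and P(2 or more) = 1 - e^(-m)(1+m). This gives 6.7%, 22.5% and 41.7% at the same rates, so the counting unit changes the picture only modestly.

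The extreme case of 4/4 has probability p^4, which is 0.01% at p = 10% and 0.8% at p = 30%.

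**The case against.** The strongest reply is that the sections can be read together: 6.5 sets the dose of the second cohort if the study goes on, while 8.5 and 4.10 decide whether it goes on. Nothing in 6.5 limits those powers. A related death or other serious related event would also reach the DSMC well before the four-patient look, since Table 4 provides that "For expedited DSMC reporting, study coordinator/research nurse must notify the DSMC via email". The upper branch already lowers the dose by 25% or 50%, and earlier experience with ATB suggests that it will rarely be needed.

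Much of this stands, and it rules out several stronger readings.

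- A reader might infer that the trial cannot be stopped for toxicity. It can, under 8.5 and 4.10.
- A reader might infer a conflict with 4.10. There is none: 4.10 is permissive, and a rule that omits stopping does not contradict a general power to stop.
- A reader might infer that there is no chance of a pause at any true DLT rate. That is true only of an explicit stop or hold within 6.5. The sequence of assessment, report to the DSMC and then second cohort implies some review between cohorts, although no enrolment hold is spelled out.
- A reader might infer that the counting unit is seriously ambiguous. The definition and both branches speak of events or DLTs, not of affected patients, so counting events is the more natural reading.

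What the reply does not remove is the wording of the upper branch. It does not say that the dose will be reduced if the study continues. It says what the committee will recommend, and that is the matter 8.5 leaves open. Nor do the earlier reports to the DSMC alter the label of safety that 6.5 attaches to a single related death.

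**Conclusion.** The point holds in a limited form. Section 6.5 contains no explicit stop or enrolment-hold outcome. At 2 or more DLTs it commits the study chairs and DSMC in advance to advice that 8.5 leaves to their judgement, and with one grade 5 DLT it still declares safety. The defect lies in the wording of the planned four-patient rule; the trial's general safety oversight is intact.

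These conclusions rest on the text and need no assumption about the DLT rate. The practical size does need one: the upper branch is reached with probability 5.2%, 18.1% or 34.8% at assumed per-patient rates of 10%, 20% or 30%, taking patients as independent. If ATB is as well tolerated as the toxicity review in 1.1 describes, the low end is the more plausible. That review also notes that the earlier trials described toxicity qualitatively and that a few patients had jaundice, so the branch cannot be dismissed. The rule is worth correcting because, if it is triggered and followed literally, it gives the less safe instruction.

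**What to change.** Reword the end of 6.5 along these lines: if 2 or more DLTs occur in the first four patients, or if any single grade 5 DLT occurs at any time, enrolment pauses pending DSMC review; the DSMC may then recommend termination, suspension, or proceeding at dose level -1 or -2, subject to 4.10 and 8.5. Make the 0-1 branch exclude a grade 5 DLT so that the two sentences agree.

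Two optional clarifications could go into the same amendment. One is to state that DLTs are counted as events, if that is the intention. The other is to point the mention of study stopping rules in 4.6 to 6.5, 4.10 and 8.5, since no rule of that name is defined elsewhere.

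The cost is one or two sentences, with no added patients, visits or samples. Enrolment is delayed only if the pause is triggered. For the count criterion alone, that chance is the probability given above for the upper branch.
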